Overall Design:	
This is a phase 1, multicenter, open-label, single-arm study to investigate the safety and tolerability of encorafenib 300 mg once daily (QD) monotherapy in adult Chinese participants with BRAF V600E mutant advanced solid tumors (unresectable metastatic melanoma or metastatic NSCLC), who are BRAF-inhibitor treatment-naïve and have failed the previous therapy(ies) for advanced metastatic disease or are not eligible to standard therapy. Participants will be eligible for the study based on identification of a BRAF V600E mutation in tumor tissue by a local National Medical Products Administration (NMPA) approved assay obtained prior to screening.
 
A dose limiting toxicity (DLT) is defined as any adverse event or abnormal laboratory value assessed as unrelated to disease, disease progression, intercurrent illness or concomitant medications/therapies resulting in the inability to tolerate at least 75% dose

	
intensity [(administered dose in mg/planned dose in mg) × 100] occurring within the first 28 days of study treatment (Cycle 1) that satisfies at least one of the predefined DLT criteria.
 
It is planned to enrol up to six evaluable participants using a 3+3 design. To be evaluable for tolerability assessment, participants must have either experienced an event meeting the DLT criteria in Cycle 1 or completed at least one cycle of study treatment and received at least 75% of the encorafenib dose intensity in Cycle 1. Non-evaluable participants, including withdrawals during Cycle 1 for reasons other than a DLT, will be replaced.
 
 • Three participants will initially be enrolled and receive encorafenib 300 mg QD, and will be evaluated for DLTs during the first cycle of treatment (28 days) [the DLT evaluation period]: 
 – If there are no DLTs in the first three participants in the DLT evaluation period, enrollment will be stopped. – If one of the first three participants experiences a DLT in the DLT evaluation period, a Trial Steering Committee (TSC) will make the recommendation whether three additional participants will be enrolled to expand the number of participants to a total of six. – If more than one of the first three treated participants experience a DLT, enrollment will be stopped. • If the group is expanded and two or more of the six participants experience a DLT, enrollment will be stopped.

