4.1.1. Study Design Overview

This is a phase 1, multicenter, open-label, single-arm study to investigate the safety and tolerability of encorafenib monotherapy in adult Chinese participants with *BRAF* V600E mutant advanced solid tumors (unresectable metastatic melanoma or metastatic NSCLC) who are *BRAF*- and *MEK*-inhibitor treatment-naïve and have failed the previous therapy(ies) for advanced metastatic disease or are not eligible to standard therapy. Participants will be eligible for the study based on identification of a *BRAF* V600E mutation in tumor tissue by a local National Medical Products Administration (NMPA) approved assay obtained prior to screening.

All participants will receive a fixed flat oral dose of 300 mg encorafenib QD.

It is planned to enrol up to six evaluable participants using a 3+3 design, shown in Figure 1.

Figure 1: Schema of 3+3 Design

Abbreviations: DLT = dose limiting toxicity; TSC = Trial Steering Committee

- Three participants will initially be enrolled and will be evaluated for DLTs during the first cycle of treatment (28 days) [the DLT evaluation period]:

- If there are no DLTs in the first three participants in the DLT evaluation period, enrollment will be stopped.
- If one of the first three participants experiences a DLT in the DLT evaluation period, a Trial Steering Committee (TSC) will make the recommendation whether three additional participants will be enrolled to expand the number of participants to a total of six.
- If more than one of the first three treated participants experience a DLT, enrollment will be stopped.
- If the group is expanded and two or more of the six participants experience a DLT, enrollment will be stopped.

A DLT is defined as any adverse event or abnormal laboratory value assessed as unrelated to disease, disease progression, intercurrent illness or concomitant medications/therapies that satisfies at least one of the criteria listed in **Table 4**.

Table 4: Criteria for Defining Dose Limiting Toxicities

Toxicity		Any of the following criteria
Blood and lymphatic system disorders[a]		≥Grade 3 neutropenia (ANC <1.0 × 10 ⁹ /L) for >7 consecutive days
		≥Grade 3 thrombocytopenia (platelets <50 × 10 ⁹ /L) for >7 consecutive days
		Grade 4 thrombocytopenia
		Febrile neutropenia (ANC < 1.0 × 10 ⁹ /L with fever ≥38.5°C)
Investigations (renal)		≥Grade 3 serum creatinine
Investigations (hepatic)		≥Grade 3 blood bilirubin (> 3 × ULN)
		≥Grade 3 ALT or AST for > 7 consecutive days

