To be evaluable for tolerability assessment by the TSC, participants must have *either* experienced an event meeting the DLT criteria during Cycle 1 *or* completed at least one cycle of study treatment and received at least 75% of the encorafenib dose intensity (administered dose in mg/planned dose in mg) in Cycle 1³.

Participants who terminate study participation for any reason other than an adverse event or abnormal laboratory value related to disease, disease progression, intercurrent illness or concomitant medications/therapies before having received at least the encorafenib dose intensity of 75% (administered dose in mg/planned dose in mg) in Cycle 1 will be considered ineligible for the safety assessment required for tolerability and will be replaced.

The TSC will analyse the available safety data and assess the toxicities as significant or not once the first three participants (and six participants if required) have fully completed the first cycle of treatment (28 days). The TSC will determine if encorafenib 300 mg QD is tolerable based on the DLT rate (DLTs observed in <33% of participants) and evaluation of the overall toxicity profile (based on deaths, treatment emergent SAEs, treatment emergent adverse events (TEAEs) leading to discontinuation and to dose interruption/reduction).

The TSC will make a recommendation if the dose of encorafenib 300 mg QD is not deemed tolerable.

³ Participants who require a dose interruption or reduction during Cycle 1 will remain evaluable for tolerability decisions if the reason for the reduction and/or interruption represents a DLT.

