9.2. Sample Size Determination

The planned sample size is up to six evaluable participants based on a 3+3 design (see Section 4.1.1). No formal sample size calculation has therefore been performed and sample size is based upon empirical considerations.

Participants will receive encorafenib 300 mg QD. This dose will be considered acceptable if the observed Cycle 1 DLT rate in evaluable participants is <33% (e.g. less than one participant with DLTs out of three participants or less than two participants with DLTs out of six participants). To be evaluable, participants must have *either* experienced an event meeting the DLT criteria in Cycle 1 *or* completed at least one cycle of study treatment and received at least 75% of the encorafenib dose intensity (administered dose in mg/planned dose in mg) in Cycle 1 (see Section 4.1.1).

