9.3. Populations for Analyses

The following populations will be analyzed:

Population	Description
Safety Set (SAF)	All participants who receive at least one dose of encorafenib (partial or full).
Dose-Determining Set (DDS)	All evaluable participants from the SAF who either achieve the minimum exposure requirement* and have sufficient safety evaluations** or experience a DLT. *Encorafenib dose intensity of 75% (administered dose in mg/planned dose in mg) in Cycle 1 **Participants must have been observed for at least 1 cycle: (≥ 28 days) following the first dose on Cycle 1 Day 1.
Pharmacokinetics Set (PK Set)	All participants who receive at least one dose of encorafenib and who have at least one postdose PK blood collection with associated bioanalytical results.

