1.2. Study Design

All participants will receive a fixed flat oral dose of 300 mg encorafenib QD.

It is planned to enrol up to six evaluable participants using an approach that is similar to a 3+3 design. The study schema is shown in the Figure 1 below:

Figure 1 Study Schema of 3+3 Design

Abbreviations: DLT = dose limiting toxicity; TSC = Trial Steering Committee

- Three participants will initially be enrolled and will be evaluated for DLTs during the first cycle of treatment (28 days) [the DLT evaluation period]:
 - If there are no DLTs in the first three participants in the DLT evaluation period, enrollment will be stopped.
 - If one of the first three participants experiences a DLT in the DLT evaluation period, a Trial Steering Committee (TSC) will make the recommendation whether three additional participants will be enrolled to expand the number of participants to a total of six.
 - If more than one of the first three treated participants experience a DLT, enrollment will be stopped.
- If the group is expanded and two or more of the six participants experience a DLT, enrollment will be stopped.
- The dose of the intervention will not be altered on the basis of the DLTs.

Sponsor Name: Pierre Fabre Médicament

Sponsor Protocol ID: W00090GE102

PII

A DLT is defined as any adverse event or abnormal laboratory value assessed as unrelated to disease, disease progression, intercurrent illness or concomitant medications/therapies that satisfies at least one of the criteria listed in Table 2.

Table 2: Criteria for Defining Dose Limiting Toxicities

Toxicity	Any of the following criteria	
Blood and lymphatic system disorders[a]	≥Grade 3 neutropenia (ANC <1.0 × 10 ⁹ /L) for >7 consecutive days	
	≥Grade 3 thrombocytopenia (platelets <50 × 10 ⁹ /L) for >7 consecutive days	
	Grade 4 thrombocytopenia	
	Febrile neutropenia (ANC < 1.0 × 10 ⁹ /L with fever ≥38.5°C)	
Investigations (renal)	≥Grade 3 serum creatinine	
Investigations (hepatic)	≥Grade 3 blood bilirubin (> 3 × ULN)	
	≥Grade 3 ALT or AST for > 7 consecutive days	
	Grade 4 ALT or AST	
	≥Grade 3 ALT or AST and ≥Grade 2 blood bilirubin	
Investigations (metabolic)	Grade 3 lipase for >7 consecutive days	
	Grade 4 lipase	
Cardiac disorders	≥Grade 3	
Gastrointestinal disorders	≥Grade 3 vomiting or nausea lasting more than 48 hours despite optimal antiemetic therapy[b]	
	≥Grade 3 diarrhea lasting more than 48 hours despite optimal treatment	
	≥Grade 3 pancreatitis	

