Participants who terminate study participation for any reason other than an adverse event or abnormal laboratory value related to disease, disease progression, intercurrent illness or concomitant medications/therapies before having received at least the encorafenib dose intensity of 75% (administered dose in mg/planned dose in mg) in Cycle 1 will be considered ineligible for the safety assessment required for tolerability and will be replaced.

The TSC will analyze the available safety data and assess the toxicities as significant or not once the first three participants (and six participants if required) have fully completed the first cycle of treatment (28 days). The TSC will determine if encorafenib 300 mg QD is tolerable based on the DLT rate (DLTs observed in <33% of participants) and evaluation of the overall toxicity profile (based on deaths, treatment emergent SAEs, TEAEs leading to discontinuation and to dose interruption/reduction).

The TSC will make a recommendation if the dose of encorafenib 300 mg QD is not deemed tolerable.

Sponsor Name: Pierre Fabre Médicament

Sponsor Protocol ID: W00090GE102

PII

Following analyses will be conducted during the study:

- First Trial Steering Committee after DLT period of the first participant. No statistical outputs will be provided.
- A Trial Steering Committee after DLT period of first 3 participants, based on subset of TFLs delivery (see Section 5.8.1) for recommendation purpose
- A Trial Steering Committee after 6 participants enrolled if TSC recommends enrolment of 3 further participants to expand number of participants to a total number of six, based on subset of TFLs delivery (see Section 5.8.1) for recommendation purpose
- Subsequent TSC meeting after all subjects have completed the safety 30 day follow-up visit. No statistical outputs will be provided.
- Final analysis at End of Study, with delivery of all planned TFLs including PK: The end of study is defined as the timepoint when the last participant enrolled has discontinued study treatment and completed the 30-day safety follow-up

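### The replacement sentence in Protocol 4.1.1 and SAP 1.2, on its natural reading, removes and replaces a participant who leaves the study early with a DLT, against the synopsis, the evaluability rule and the DDS

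*Protocol*

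**What the plan says.** **Replacement sentence (Protocol 4.1.1; same wording in SAP 1.2).** It begins "Participants who terminate study participation for any reason other than an adverse event or abnormal laboratory value related to disease, disease progression" and continues with intercurrent illness and concomitant medication or therapy. Those who leave for any other reason before reaching 75% of the Cycle 1 dose intensity "will be considered ineligible for the safety assessment required for tolerability and will be replaced".

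**DLT definition (Protocol 4.1.1 and 9.4.2; SAP 1.2 and 5.3.1).** "A DLT is defined as any adverse event or abnormal laboratory value assessed as unrelated to disease, disease progression, intercurrent illness or concomitant medications/therapies", provided that a listed toxicity criterion is met.

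**Evaluability rule (Protocol 4.1.1 and 9.2; SAP 1.2 and 3).** A participant is evaluable on either of two grounds. The first is having "experienced an event meeting the DLT criteria during Cycle 1". The second is completing at least one cycle with at least 75% of the dose intensity. A further note (footnote 3 in Protocol 4.1.1, body text in SAP 1.2) keeps participants evaluable when a DLT is the reason for an interruption or reduction. It does not mention leaving the study.

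**Synopsis (Protocol 1.1).** "Non-evaluable participants, including withdrawals during Cycle 1 for reasons other than a DLT, will be replaced".

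**DDS (Protocol 9.3; SAP 4.2).** It contains evaluable treated participants who either meet the exposure and observation minimum or have a DLT.

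**Decision rule (Protocol 9.2; SAP 3).** The dose is acceptable if the observed Cycle 1 DLT rate in evaluable participants is below 33%. The examples given are fewer than one in three, or fewer than two in six.

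**The concern.** The replacement sentence excepts leavers whose event is *related* to four causes. The DLT definition requires the event to be *unrelated* to the same four causes. A DLT leaver therefore falls outside the exception and is declared ineligible and replaced, although the paragraph directly above in Protocol 4.1.1 makes that same participant evaluable.

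The stake is the count behind the primary endpoint. With three to six participants, a single DLT decides whether the rate is acceptable. Replacement is an enrolment decision, taken before the final analysis set is fixed. A reader of Protocol 4.1.1 or SAP 1.2 alone has two opposite instructions a few lines apart.

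There is also a gap on the other side. The sentence does not say what happens to the leavers it excepts, for example those with an event related to disease progression. Without a DLT, a completed cycle and 75% of the dose they are non-evaluable under the evaluability rule, and the synopsis replaces non-evaluable participants.

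**Working it through.** **1. The plan's own threshold.** 0/3 = 0% and 1/6 = 16.7% pass. 1/3 and 2/6 = 33.3% fail. This reproduces the examples in Protocol 9.2 and SAP 3.

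**2. What 75% means.** SAP 5.6.1 sets the planned Cycle 1 dose at 8400 mg (28 × 300 mg). 0.75 × 8400 = 6300 mg, or 21 full daily doses.

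**3. A worked case.** Four participants are treated. One leaves the study on Day 10 with a DLT, having received at most 10 × 300 = 3000 mg (3000/8400 = 35.7%). The other three complete Cycle 1 without a DLT.

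| Rule followed | Count | Against <33% |
|---|---|---|
| Evaluability rule and synopsis: leaver is one of the first three | 1/3 = 33.3% | not met; the Trial Steering Committee (TSC) considers expansion |
| Replacement sentence as worded: leaver removed and replaced | 0/3 = 0% | met; enrolment stops |
| Leaver replaced, but kept in the DDS | 1/4 = 25% | met, on a denominator that Protocol 9.2 does not exemplify |

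In an expanded group, 2/6 becomes 1/6 = 16.7% by the same route, or 2/7 = 28.6% if the leaver is replaced and also kept. Both are below 33%. Retention in the DDS therefore does not undo a wrong replacement.

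**4. Size over repeated trials (illustration).** The documents give neither input, so both are assumed:
- p, the true Cycle 1 DLT probability;
- f, the share of DLT participants who leave before 75% and are replaced.

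If the sentence is always applied as worded, the DLT probability among counted participants is p′ = p(1−f)/(1−pf). With q = 1−p′, and the TSC always expanding after 1/3:

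P(acceptable rate) = q³ + 3p′q² × q³.

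For p = 1/3 and f = 0: 0.2963 + 0.4444 × 0.2963 = 0.428. For p = 1/3 and f = 0.05: p′ = 0.3167/0.9833 = 0.322, q = 0.678, giving 0.3116 + 0.4441 × 0.3116 = 0.450.

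| p | f = 0 | f = 5% | f = 10% | f = 25% |
|---|---|---|---|---|
| 20% | 70.9% | 72.6% | 74.4% | 79.8% |
| 33.3% | 42.8% | 45.0% | 47.3% | 55.1% |
| 50% | 17.2% | 18.7% | 20.3% | 26.5% |

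If the TSC never expands, P = q³. At p = 33.3% this gives 29.6%, 31.2%, 32.8% and 38.5%.

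The chance that at least one DLT participant is replaced while the first three places are filled is 1−(1−pf)³. At p = 33.3% this is 4.9% (f = 5%), 9.7% (f = 10%) and 23.0% (f = 25%).

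**The case against.** **Most of the text points the other way.** The evaluability paragraph is expressly about the TSC's assessment, so it governs the TSC count as well as the final DDS. The enrolment rules count DLTs among the first three participants, without the word evaluable. SAP 5.3.1 identifies DLTs from the case report form flag, not from replacement status. A TSC meeting follows the first participant's DLT period (SAP 1.2), and SAP 5.2 reports treatment discontinuation due to DLT. The TSC also weighs deaths, SAEs and discontinuations. The TSC Charter, which is not among the documents, may add procedure. All this stands, and it makes misapplication less likely. It does not remove the contrary instruction. SAP 6.8 also names insufficient exposure after premature withdrawal as a ground for exclusion from analysis sets, with no DLT exception stated there.

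**The trigger is rare.** Participants who stop treatment still have an end of treatment visit and a 30-day follow-up (Protocol 7.1.2), and withdrawal from the study is expected to be uncommon (Protocol 7.2). This stands too. The route is nevertheless open: Protocol 7.2 lets the investigator withdraw a participant for safety, which ends both treatment and study.

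**The sentence can be parsed differently.** If an adverse event and disease progression are read as separate exceptions, DLT leavers are spared. This is strained, because the same four-cause list follows *unrelated to* in the DLT definition.

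**A stronger reading that fails.** A reader might infer that the sentence forbids replacing progression leavers, so that every parse contradicts the synopsis and the TSC could be left with two informative participants. The documents do not support that. The sentence says who is replaced and is silent on the rest; the evaluability rule and the synopsis fill the gap.

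**Conclusion.** The contradiction is real and is present in both documents. On its natural reading, the replacement sentence removes a DLT participant whom the synopsis, the evaluability rule and the DDS keep. It should be fixed, but it is a narrow fault: it needs a DLT, exit from the study, and less than 75% of the Cycle 1 dose.

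In the individual case the effect is decisive: 1/3 becomes 0/3, or 2/6 becomes 1/6. On average it is modest if early exit is rare. At p = 33.3% with expansion always following 1/3, the chance of an acceptable rate moves from 42.8% to 45.0% (f = 5%) or 47.3% (f = 10%). These figures rest on assumed p and f, and on the sentence being applied every time over the adjacent paragraph.

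Two further inferences are not supported. The 55.1% at f = 25% is not a worst case, because the word uncommon in Protocol 7.2 sets no bound on f. And a reader might take the DDS definition to protect the final analysis fully. It does not once a replacement has been enrolled, as the 1/4 = 25% count shows.

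**What to change.** Reconcile Protocol 1.1, 4.1.1 and 9.3 with SAP 1.2 and 4.2 by replacing the sentence in Protocol 4.1.1 and SAP 1.2 with:

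> A participant with a DLT in Cycle 1 is evaluable, stays in the DDS and is not replaced, whatever the dose intensity received or the time of leaving. A participant without a Cycle 1 DLT who leaves the study during Cycle 1, or who receives less than 75% of the planned Cycle 1 dose, for any reason, is non-evaluable and is replaced.

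This also settles the position of progression leavers. Merely changing *related* to *unrelated* would not be enough: leavers with drug toxicity short of a DLT would then fall in the exception, although the synopsis and the DDS make them non-evaluable. The sponsor should confirm that replacing those participants is intended.

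The synopsis DLT definition adds inability to tolerate at least 75% dose intensity. Protocol 4.1.1 and SAP 1.2 do not carry that condition. These passages must be reconciled as well.

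The cost is one reworded sentence in each document and one aligned definition. The 33% threshold, the analysis sets and all other analyses stay unchanged.

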		Grade 4 ALT or AST
		≥Grade 3 ALT or AST and ≥Grade 2 blood bilirubin
Investigations (metabolic)		Grade 3 lipase for >7 consecutive days
		Grade 4 lipase
Cardiac disorders		≥Grade 3
Gastrointestinal disorders		≥Grade 3 vomiting or nausea lasting more than 48 hours despite optimal antiemetic therapy[b]
		≥Grade 3 diarrhea lasting more than 48 hours despite optimal treatment
		≥Grade 3 pancreatitis
Skin and subcutaneous tissue disorders[c]: rash, photosensitivity or HFSR		Grade 3 rash/photosensitivity/HFSR for >7 consecutive days despite skin toxicity treatment (as per local practice)
		Grade 4 rash/photosensitivity/HFSR
General disorders and administration site conditions		Grade 3 fatigue/asthenia for >7 consecutive days
Ophthalmologic	Uveitis	Grade 3 for >21 consecutive days confirmed by ophthalmologic examination

Toxicity		Any of the following criteria
		Grade 4 confirmed by ophthalmologic examination
Any other eye disorders	Grade 3 for >21 consecutive days	
	Grade 4	
Other adverse events[d]		≥Grade 3 adverse events (excluding SCC)

Abbreviations: ALT = alanine aminotransferase; ANC = absolute neutrophil count; AST = aspartate aminotransferase; DLT = limiting dose toxicity; HFSR = hand-foot skin reaction (also known as palmar-plantar erythrodysesthesia [PPE] syndrome); NCI CTCAE = National Cancer Institute Common Terminology Criteria for Adverse Events; ULN = Upper limit of normal.

Grades according to NCI CTCAE grading system.

- [a] ≥Grade 3 anemia will not be considered a DLT unless judged to be a hemolytic process secondary to study treatment. ≥Grade 3 lymphopenia will not to be considered a DLT unless clinically significant.
- [b] Optimal therapy for vomiting or diarrhea will be based on study site guidelines with consideration of the prohibited medications listed in this protocol.
- [c] Squamous cell carcinoma reported to be an on-target side-effect that was manageable will not be considered a DLT.
- [d] An adverse event must be clinically significant to be defined as a DLT: alopecia, study treatment-related fever, electrolyte abnormalities (including K, NA, Cl, HCO₃, Mg, Ca, PO₄) that are ≤Grade 3 abnormalities will not be considered a DLT unless clinically significant.

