Urinalysis	Appearance, color Specific gravity Blood, glucose, leukocytes, ketones, pH, protein by dipstick Microscopic examination (if blood or protein abnormal)
Serology (screening only)	
 Hepatitis B: HBsAg, HBsAg antibody, hepatitis B core antibody, and HBV DNA if HBsAg or HBcAb was positive HCV Ab and HCV RNA if HCV Ab was positive HIV
Postmenopausal status (screening only, if required)	FSH

Abbreviations: Ab = antibody; aPPT = activated partial thromboplastin time; ALT = alanine aminotransferase; AST = aspartate aminotransferase; BUN = blood urea nitrogen; CK = creatine kinase; DNA = deoxyribonucleic acid; FSH = follicle stimulating hormone; GGT = gamma glutamyl transferase; HBsAg = hepatitis B surface antigen; HBV = hepatitis B virus; HCV = hepatitis C virus; HIV = human immunodeficiency virus; INR = international normalized ratio; LDH = lactate dehydrogenase; pH = hydrogen ion concentration; PT = prothrombin time; RBC = red blood cell(s); RNA = ribonucleic acid; SAE = serious adverse event; ULN = upper limit of normal; WBC=white blood cell.
 
[a] Details of liver clinical chemistry stopping criteria and required actions and follow-up assessments after liver stopping or monitoring event are given in Appendix 10.4. All events of ALT $>3 \times$ ULN and bilirubin $>2 \times$ ULN ($>35\%$ direct bilirubin) or ALT $>3 \times$ ULN and INR >1.5, if INR measured which may indicate severe liver injury (possible Hy's Law), must be reported as an SAE.
	

The investigator must review the laboratory report, document this review and record any clinically relevant changes occurring during the study as an adverse event. The laboratory reports must be filed with the source documents. Clinically significant abnormal laboratory findings are those which are not associated with the underlying disease, unless judged by the investigator to be more severe than expected for the participant's condition. An abnormal laboratory value that is not associated with an already reported adverse event is to be recorded as an adverse event only if an action on the study treatment is made as a result of the abnormality, if treatment for management of the abnormality is required or at the discretion of the investigator.

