AST or ALT 3.0 to $5.0 \times ULN$ AND blood total bilirubin $>2.0 \times ULN$	
Interrupt dosing of encorafenib until resolved to Grade ≤ 1, then:
 
 • If resolved in ≤ 7 days, resume study treatment at one reduced dose level[a] of encorafenib. • If not resolved in ≤ 7 days, permanently discontinue encorafenib.

Worst Toxicity NCI CTCAE Version 4.03 Grade (unless otherwise specified)	Dose Modification for Encorafenib
Grade 3 AST or ALT >5.0 to $8.0 \times$ ULN AND blood total bilirubin $\leq 2.0 \times$ ULN	
Interrupt dosing of encorafenib until resolved to Grade ≤ 1 (or Grade ≤ 2 in case of liver metastasis), then:
 
 • If resolved in ≤ 14 days, resume study treatment at current dose level of encorafenib. • If not resolved in ≤ 14 days, resume study treatment at one reduced dose level[a] of encorafenib. 
If additional occurrence: Interrupt dosing of encorafenib until resolved to Grade ≤ 1 (or Grade ≤ 2 in case of liver metastasis), then resume treatment at one reduced dose level[a] of encorafenib.

AST or ALT $>8 \times$ ULN AND blood total bilirubin $\leq 2.0 \times$ ULN	Permanently discontinue encorafenib.
AST or ALT $>5.0 \times$ ULN AND blood total bilirubin $>2.0 \times$ ULN	Permanently discontinue encorafenib.
Grade 4 AST or ALT $>20.0 \times$ ULN	Permanently discontinue encorafenib.
Cardiac investigation – Prolongation of QT interval QTcF value	

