4.2. Dose-Determining Set (DDS)

All evaluable participants from the SAF who either achieve the minimum exposure requirement* and have sufficient safety evaluations** or experience a DLT.

*Encorafenib dose intensity of 75% (administered dose in mg/planned dose in mg) in Cycle 1

**Participants must have been observed for at least 1 cycle: (≥ 28 days) following the first dose on Cycle 1 Day 1.

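### Cycle 1 drug toxicity that Table 19 answers with a permanent stop or long hold can meet no Table 4 DLT criterion, so the participant can be replaced and drop out of the DLT rate

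*Protocol*

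**What the plan says.** **Evaluability.** Protocol 4.1.1 and 9.2 (repeated in SAP 1.2 and 3) count a participant as evaluable after a Cycle 1 DLT, or if he or she "completed at least one cycle of study treatment and received at least 75% of the encorafenib dose intensity". Footnote 3 of Protocol 4.1.1 adds that someone with an interruption or reduction "will remain evaluable for tolerability decisions if the reason for the reduction and/or interruption represents a DLT".

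**Replacement.** The Synopsis says: "Non-evaluable participants, including withdrawals during Cycle 1 for reasons other than a DLT, will be replaced". Protocol 4.1.1 and SAP 1.2 word it differently. They replace people who leave before reaching 75% for any reason except events due to disease, progression, intercurrent illness or other therapy. On that wording, people who leave because of drug toxicity are replaced.

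**Analysis set.** The Dose-Determining Set (DDS) in SAP 4.2 and Protocol 9.3 is "All evaluable participants from the SAF who either achieve the minimum exposure requirement" and were observed for at least 28 days, or had a DLT. The primary DLT summary uses the DDS (SAP 5.3.2). SAP 5.3.3 and 5.3.4 plan no sensitivity or supplementary analysis.

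**Decision rule.** Protocol 9.2 and SAP 3 call the dose acceptable if the DLT rate in evaluable participants is below 33%. Protocol 4.1.1 and 9.7 have the Trial Steering Committee (TSC) judge tolerability on that rate together with the overall toxicity profile.

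**Toxicity tables.** Table 4 (Protocol 4.1.1) defines DLTs by grade and often by duration. Table 19 (Protocol 10.4) sets holds and permanent stops by its own thresholds.

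**The concern.** The primary endpoint is meant to show whether 300 mg QD can be taken through Cycle 1. If drug toxicity obliges a participant to stop but is not a DLT, that participant fails the 75% requirement and leaves both the numerator and the denominator. A replacement who tolerates the dose then takes the place. The exclusion depends on the outcome being measured and works in one direction, towards a lower DLT rate. With three to six participants, one exclusion can change which branch of the 3+3 scheme is followed.

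**Working it through.** **1. The plan's own figures.** SAP 5.6.1 gives a planned Cycle 1 dose of 8400 mg, and 28 x 300 = 8400 reproduces it. The threshold is 0.75 x 8400 = 6300 mg, and 6300/300 = 21 full doses. The <33% rule also behaves as Protocol 9.2 describes: 0/3 = 0% and 1/6 = 16.7% pass; 1/3 and 2/6 = 33.3% fail.

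**2. Table 19 against Table 4.**

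- *ALT/AST 3 to 5 x ULN with bilirubin above 2 and up to 3 x ULN (for example 4 and 2.5).* Table 19 interrupts dosing and, if unresolved after 7 "days, permanently discontinue encorafenib". Table 4 needs bilirubin above 3 x ULN, or Grade 3 or higher ALT/AST combined with Grade 2 or higher bilirubin, or Grade 3 or higher ALT/AST for more than 7 days, or Grade 4 ALT/AST. None is met. The catch-all row for other adverse events starts at Grade 3 and does not reach it either. Under Table 8 note [a], ALT above 3 x ULN with bilirubin above 2 x ULN and more than 35% direct bilirubin "must be reported as an SAE". So a possible Hy's Law case can be outside the DLT definition.
- *ALT/AST above 8 and up to 20 x ULN with bilirubin below Grade 2.* Table 19 stops treatment permanently with no duration condition. Table 4's row for at least "Grade 3 ALT or AST for" more than 7 consecutive days is not met if the value falls below Grade 3 within 7 days. If it stays at Grade 3 for longer, the event is a DLT and the participant is evaluable.
- *Grade 3 uveitis lasting 21 days or less.* Table 19 holds dosing until Grade 1 or better. Table 4 requires "Grade 3 for >21 consecutive days confirmed by ophthalmologic examination", or Grade 4. Twenty-two consecutive days fit inside Days 1 to 28 only with onset by Day 7 (28 - 22 + 1 = 7).

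The second and third cases are gaps only if the catch-all row is read as not covering toxicities that have their own row. The first is a gap on either reading.

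**3. When the participant becomes non-evaluable.**

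- Permanent stop before the Day 15 dose (Day 15 is a scheduled chemistry visit): 14/28 = 50%.
- Permanent stop before the Day 21 dose: 20/28 = 71.4%. Before the Day 22 dose: 21/28 = 75%.
- Any 8-day hold with 300 mg resumed: 20/28 = 71.4%.
- An 8-day hold from Day 8 with 225 mg resumed: (7 x 300 + 13 x 225)/8400 = 5025/8400 = 59.8%.

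From Day 22 a permanent stop keeps at least 75%. Protocol 4.1.1 (cycle completed) and the DDS (observed for 28 days) can then disagree on evaluability. The event is not a DLT either way.

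**4. Effect on the rule.** Suppose one of the first three is such a case and nobody else has a DLT. Counted as not tolerating the dose: 1/3 = 33.3%, which fails <33% and goes to the TSC for an expansion decision. Replaced: 0/3 = 0%, which passes, and enrolment stops. If the case is added back after the replacement has been treated, the figure is 1/4 = 25%, so the denominator must be stated.

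**5. Size under assumed rates.** Let p be the probability of a DLT and q the probability of a non-DLT intolerance that leads to replacement. The documents give neither. Assume independent participants and that the TSC always expands after 1/3. The chance of meeting the rule is A(x) = (1 - x)^3 + 3x(1 - x)^5, with x = p/(1 - q) if such cases are replaced and x = p + q if they are counted.

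| p | q | Replaced | Counted |
|---|---|---|---|
| 5% | 5% | 97.1% | 90.6% |
| 10% | 10% | 88.7% | 70.9% |
| 10% | 20% | 86.2% | 49.4% |
| 20% | 20% | 60.0% | 30.9% |

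The chance of at least one such case among the first three treated is 1 - (1 - q)^3: 14.3%, 27.1% and 48.8% for q = 5%, 10% and 20%.

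**The case against.** A reader might infer that these participants disappear from the dose decision. They do not. The TSC also weighs deaths, serious events and events leading to discontinuation, interruption or reduction (Protocol 4.1.1 and 9.7, SAP 5.8.1), and could find the dose not tolerable at 0/3. Stopping enrolment at 0/3 is not in itself a finding of tolerability. The Safety Set tables keep these participants, SAP 5.1 flags those excluded from the DDS, SAP 6.8 lists reasons for exclusion, and SAP 5.6.1 lists Cycle 1 relative dose intensity. This stands, and it confines the problem to the primary rate and its numerical rule. It does not remove it: Protocol 9.2 ties acceptability to that rate alone, and no planned analysis shows the rate with these participants restored. Which outputs reach the TSC is set in documents not available here.

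A reader might also take all three cases as certain gaps. Table 4 asks for at least one criterion to be met and does not limit the catch-all row, so Grade 3 transaminase or uveitis events could fall under it. That reading would empty the duration limits in the specific rows of meaning, but the text does not settle the matter.

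Table 19 is headed as recommended, and Protocol 6.6 allows clinical judgment and may exempt transient laboratory values of up to 72 hours from dose reduction rules. An abnormality unresolved after 7 days is not transient in that sense.

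Finally, the events may be rare. The DLTs and common events that Protocol 2.1.4 lists for encorafenib monotherapy include no hepatic or uveitis event. Those lists are not exhaustive, but they give no support for any particular value of q.

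**Conclusion.** The point holds in this form. Table 19 can require a permanent stop or prolonged hold in Cycle 1 for drug toxicity that meets no Table 4 criterion. If fewer than 21 full doses' worth is then taken, the participant is non-evaluable and, under the Synopsis, replaced. The combined liver case (ALT/AST 3 to 5 x ULN, bilirubin above 2 and up to 3 x ULN, unresolved after 7 days) follows from the text on any reading. The other liver case and the uveitis case depend on the scope of the catch-all row. For someone on hold who stays in the study, replacement rests on the Synopsis, because the Protocol 4.1.1 sentence concerns people who leave.

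The bias runs towards acceptability. One case can mean 0/3 in place of 1/3. The acceptance probabilities above rest on assumed p and q and on automatic expansion; they show direction and possible scale, not an expected effect. The documents do not support saying that such cases will be common, that the TSC would be unaware of them, or that they ought to be classed as DLTs.

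**What to change.** 1. Reconcile Table 4, Table 19, the evaluability and replacement text (Synopsis, Protocol 4.1.1 and 9.2, SAP 1.2 and 3) and the DDS definition (Protocol 9.3, SAP 4.2). State whether the catch-all row covers toxicities with their own row, whether a participant who leaves because of drug toxicity is replaced, and whether completing or being observed for Cycle 1 is the requirement. Which clinical rule is right is for the sponsor and investigators; no change to a Table 19 action or to the DLT definition is proposed here.

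2. In SAP 5.3.3 or 5.3.4, and in the TSC outputs, add a supplementary analysis. It should identify every treated participant left out of the DDS or replaced because of an event not attributed to disease, progression, intercurrent illness or concomitant therapy. It should show the Cycle 1 DLT rate with and without them counted as not tolerating the dose, beside the <33% rule. Give the rate with the original participant in place of the replacement (1/3 in the example) and for all treated (1/4), since the two can fall on different sides of 33%.

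The cost is wording changes and one small table. The supplementary rate may be less favourable than the primary one.
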